#### 9. STATISTICAL METHODS

All data collected during this study will be presented in subject data listings. All statistical analyses will be performed using SAS® for Windows, version 9.4 or later.

## 9.1 Summarizing and Tabulating the Collected Data

All data collected will be summarized according to the variable type:

- Continuous data summaries will include number of observations, mean, standard deviation, median, and minimum and maximum values.
- Categorical data summaries will include frequency counts and percentages.

# 9.1.1 Subject Disposition and Withdrawals

The disposition of all subjects who sign an ICF will be provided. The number of subjects screened, screen failure, randomized, received at least one treatment, completed, and discontinued during the study, as well as the reasons for all post treatment discontinuations will be summarized. Disposition and reason for study discontinuation will also be provided as a by-subject listing.

#### 9.1.2 Protocol Deviations

Protocol deviations will be identified and classified as minor or major before un-blinding.

Protocol deviations for all randomized subjects will be listed as by-subject listing and major deviations will be summarized descriptively according to the following categories:

- Did not meet Inclusion/Exclusion criteria but entered into study
- · Developed withdrawal criteria during the study but not withdrawn
- · Received excluded concomitant medication
- Study treatment dosing deviation

# 9.1.3 Demographics and Baseline Characteristics

Demographics and baseline characteristics (i.e., Age, Race, Gender etc.) will be summarized using appropriate descriptive statistics.

Medical history of the subjects will also be summarized and also provided as a by-subject listing.

# 9.1.4 Prior and Concomitant Medications

Prior and concomitant medications will be summarized for the Safety population. All prior and concomitant medications recorded in the eCRFs will be coded to generic term and all matching Anatomic Therapeutic Classification (ATC) codes using WHO Drug Summaries will be prepared using the coded terms. All prior and concomitant medications recorded in the eCRFs will also be listed.

#### 9.1.5 Treatment Exposure

All data from administration of study drug will be listed and summarized.

# 9.2 Analysis of Efficacy Data

The primary analysis will be conducted on the mITT population. The PP population will be used as a supportive analysis if there is at least 5% difference between the numbers of subjects in the two populations. All statistical tests for efficacy will be two-sided tests, with  $\alpha$ =0.05

# 9.2.1 Primary Efficacy Endpoint

The primary endpoint for the study is all-cause mortality at Day 28. All-cause mortality at Day 28 will be summarized. The estimated difference in mortality rates along with 95% confidence interval and p-value will be calculated using Logistic Regression adjusting for stratification factors (Ge et al. 2011).

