8.9.2. Covariates

For efficacy analyses important prognostic factors that need adjustment will be specified in the Statistical Analysis Plan (SAP) for the study

CONFIDENTIAL Page 81 of 108

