8.10. ANALYSIS METHODS

A Statistical Analysis Plan (SAP) will be developed and approved before the database is locked. The SAP will present the detailed statistical methodology to be used in analyzing the data from this trial.

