#### 2.5 STRATIFICATION

Randomization will be stratified into one of the three categories based on clinical status of the patient at baseline:

- Hospitalized, not in intensive care unit (ICU)
- Hospitalized, in ICU, on mechanical ventilation, not on vasopressors
- Hospitalized, in ICU, on mechanical ventilation, on vasopressors

For the purpose of stratification, on vasoporessors dose is defined as: norepinephrine  $>20\mu g/min$  and/or vasopressin>0.04 units/kg/min.

Subjects will also be stratified for the prior use of off-label immunomodulatory treatments for COVID-19.

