#### 2.7.3 Final Analysis

Treatment unblinding and release of the randomization codes of the investigational product assignments for the study will occur immediately following database lock when all randomized subjects have completed the study or discontinued from the study and after all clinical data have been received and data inconsistencies have been resolved.

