#### 4. SAMPLE SIZE DETERMINATION AND RATIONALE

This is a randomized study with two treatment groups. The subjects will be randomized to the treatment groups (leronlimab or placebo) in a 2:1 ratio.

A total of three hundred ninety (390) subjects will be randomized in a 2:1 ratio to leronlimab or placebo groups with the goal of having 369 subjects (246 subjects in the leronlimab and 123 in the placebo group) complete the study.

The sample size is obtained based on the assumption that there will be a clinically meaningful difference in the rate of Day 28 mortality (i.e., 15% which is 45% Day 28 mortality rate for the placebo group versus 30% Day 28 mortality rate in the leronlimab group). This sample size is based on using a 2-sided Z-test with 80% power and an overall significance level of 0.05. The expected

dropout rate is 5%. To accommodate subject attritions due to the potential discontinuations, it is recommended randomizing an estimated 390 subjects (260 in the leronlimab group and 130 placebo group). Sample size is estimated using PASS sample size software, tests for two proportions.

A single arm, non-randomized, open-label phase is added to the protocol after completion of enrollment in the Randomized Phase of the study in order to provide access to leronlimab for the eligible patients. Approximately, 100 subjects are expected to be enrolled in the non-randomized phase. Enrollment will remain open until the decision is made by Sponsor and/or FDA to close the recruitment. No statistical power calculation is used for the sample size calculation for the non-randomized portion of the trial.

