## 8.5 Subgroups

Subgroup analyses will be conducted to evaluate whether the treatment effects are consistent across different subgroups as following. All subgroup analyses will be considered exploratory, except for some that were prespecified in the protocol for specific reasons.

- 1. Based on baseline Ordinal Scale
- Baseline ordinal scale of Score 2 Critical patients;
- Baseline ordinal scale of Score 3 Severe patients;
- Baseline ordinal scale of Score 4 Severe patients;
- Baseline ordinal scale of Score 3 and 4 Severe patients;
- 2. Based on age group
- Age < 40
- 40 <= Age <= 65
- Age > 65
- 3. Based on Dexamethasone use
- 4. Laboratory parameters such as, CD4/CD8 ratio and IL-6

In addition, the study allowed co-administration of any off-label COVID-19 treatments. Hence, subgroup analyses will be performed to evaluate whether the treatment effects are consistent without and with the different co-administered off-label treatments including but not limited to hydroxychloroquine or chloroquine with or without azithromycin, remdesivir, dexamethasone (or other corticosteroids), monoclonal antibodies (such as bamlanivimab, casirivimab, imdevimab, siltuximab), immunomodulatory agents (such as baricitinib, sarilumab, clazakizumab, tocilizumab, anakinra), convalescent plasma therapy.

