#### 8.7 Standard Calculations and Conventions

#### 8.7.1 Age

Age will be calculated as the number of completed years between the date of informed consent and the subject's birth date.

Age (years) = integer of 
$$[(date of informed consent - date of birth)/365.25]$$

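### The primary Day 28 mortality model adjusts only for the stratification factors; adding age, already collected for every patient, would gain modest precision at almost no cost

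*SAP*

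**What the plan says.** SAP 9.2.1 defines the primary analysis of all-cause mortality at Day 28. The estimated risk difference, 95% confidence interval and p-value "will be calculated using Logistic Regression adjusting for stratification factors", with a citation to a method for covariate-adjusted differences in proportions. No other covariate is named.

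SAP 2.5 gives the factors as a three-level clinical status (not in ICU; ICU and ventilated without vasopressors; ICU and ventilated with vasopressors) and a second factor: "Subjects will also be stratified for the prior use of off-label immunomodulatory treatments for COVID-19". Protocol 8.5 adds region if multinational sites take part. Age appears in neither list.

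Protocol 8.9.2 passed the decision to the SAP: "For efficacy analyses important prognostic factors that need adjustment will be specified in the Statistical Analysis Plan (SAP) for the study".

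Age is available. Protocol 3.3.1 makes it an eligibility criterion, Protocol 7.3 collects date of birth, and SAP 8.7.1 derives it: "Age will be calculated as the number of completed years between the date of informed consent". The SAP then uses age for the baseline summaries (9.1.3) and for a subgroup analysis (8.5, "Based on age group"), but not as a covariate. The sensitivity analyses in SAP 8.6 do not name an age-adjusted model.

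**The concern.** When a baseline variable predicts the outcome, adding it to the model shrinks the variance of the treatment estimate without changing what is estimated. The strata describe acute severity in coarse steps. All patients outside the ICU share one level, and entry is open from 18 years with no upper limit, so age may explain variation in mortality that the strata do not.

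Bias, type I error and a power shortfall are not at stake. The sample size rests on a "2-sided Z-test with 80% power and an overall significance level of 0.05", which uses no covariates. The stake is the width of the confidence interval and a small amount of power on a mortality endpoint, from data already in hand.

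**Working it through.** **1. Reproduce the planned sample size.** Inputs from SAP 4: 45% versus 30%, 2:1 allocation, two-sided 0.05, 80% power, 5% dropout.

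- Unpooled Z-test, placebo arm: n = (1.960 + 0.842)² × (0.45 × 0.55 + 0.30 × 0.70 / 2) / 0.15² = 122.97, so 123 placebo and 246 leronlimab, 369 in total. This matches the plan.
- Dropout: 369 / 0.95 = 388.4, so 389; the plan rounds to 390 (260 + 130).
- Power at 123/246 is 80.0% unpooled and 80.9% pooled; at 130/260 it is 82.9% pooled.

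The planned figure holds and does not depend on age.

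**2. Main simulation.** 390 patients, 2:1, blocks of 3 within clinical status × immunomodulator use × region. Each trial is analysed with a logistic model, a standardised risk difference, a delta-method standard error and a Wald test at 1.96. There are 20,000 trials per scenario at 45% versus 30%, and 20,000 under the null (35% in both arms).

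The following are assumptions, not figures from the documents:

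- age mean 60, SD 13
- baseline ordinal score 2/3/4 in 20/30/50%, with a quarter of Score 2 patients on vasopressors
- prior immunomodulator use 30%; regions 80/20
- unventilated ICU patients coded as non-ICU
- odds ratio for death per decade of age 1.0, 1.2, 1.5 or 1.8 (none, weak, moderate, strong), with the effects of ordinal score and vasopressor use set to rise alongside.

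| Age effect | Variance ratio, with age / strata only | Power, strata only → with age | Size-adjusted power | Null rejection, strata only / with age |
|---|---|---|---|---|
| None | 1.003 | 82.7 → 82.7% | 82.0 → 81.9% | 5.33 / 5.36% |
| Weak | 0.991 | 82.7 → 83.2% | 81.6 → 82.1% | 5.63 / 5.51% |
| Moderate | 0.949 | 83.2 → 85.2% | 82.3 → 84.3% | 5.54 / 5.45% |
| Strong | 0.904 | 84.7 → 88.0% | 84.1 → 87.3% | 5.33 / 5.42% |

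The Monte Carlo standard error of the null rates is 0.16 points. Size-adjusted power uses each model's own empirical null cut-off and shows a similar gain, so the gain is not disguised size inflation.

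**3. Convert to patients.** Equivalent extra patients = 390 / ratio − 390:

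- weak: 390 / 0.991 − 390 ≈ 4
- moderate: 390 / 0.949 − 390 ≈ 21
- strong: 390 / 0.904 − 390 ≈ 41

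**4. Vary the assumptions.** At moderate strength, an age effect that is flat below 55 years gives a ratio of 0.937. Making ventilated patients 5 years older gives 0.949. Age in the three SAP 8.5 groups instead of a linear term gains less (1.006, 0.997, 0.965, 0.932 across the four scenarios). Adding region to the strata-only model leaves the ratio at 1.000.

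**5. Cross-checks.** A separate simulation with 246/123 completers and one binary stratum (3,000 trials per scenario) gave variance cuts of about 1%, 2-3%, 10% and 13-14% for odds ratios of 1.25, 1.5, 2.0 and 2.5 per SD of age. On that scale the odds ratios per decade above are 1.2^1.3 ≈ 1.27, 1.5^1.3 ≈ 1.69 and 1.8^1.3 ≈ 2.15, so the two agree. Without age the mean estimate was -0.149 to -0.152 against a true -0.15, and null rejection was 4.6-5.8%. A third simulation (390 patients, blocks of 3 within strata, 4,000 trials per scenario) gave ratios of 1.00, 0.99, 0.94 and 0.90, power changes of about 0, 0, +1.5 and +3.6 points, and null rejection of 4.7-5.7%.

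**The case against.** The plan contains no error here. Adjusting for the randomisation strata is a complete, pre-specified choice, and it can be read as the SAP's answer to Protocol 8.9.2. That stands, and it is why this is an efficiency point only.

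No passage says age predicts Day 28 mortality; SAP 8.5 lists age groups only to check consistency of the treatment effect. The protocol does describe SOFA as a predictor of ICU mortality and NEWS2 as a measure of degree of illness. It follows that the documents cannot fix the gain, which could be zero. SOFA is scheduled only for intubated patients. NEWS2 is scheduled for all randomised patients but was not assessed here. Neither fact counts against age: a non-prognostic age term costs 0.3% in variance.

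Timing is the strongest objection. Randomised enrolment was complete when the open-label phase was added, the SAP is at Version 7.0 after regulatory correspondence, and an unblinded interim at 50% is planned on a Z from a logistic model whose covariates SAP 5.2.5 does not name. A late change to the primary model invites questions about data-driven choice, and the interim and final statistics could differ in their covariates. The simulations contain no interim or sample-size increase, so that interaction is unexamined. The change is therefore acceptable only before lock and with the functional form fixed.

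**Conclusion.** The point holds as a recommended improvement to a valid analysis. Age is absent from the primary model, it should be known for every randomised patient, and using it would keep the same risk-difference estimand. The gain ranges from nothing to about a 10% cut in variance and about 3 points of power under the main assumptions. The moderate case is 5% and 2 points, on a design that already exceeds 80% power at 390 patients. The range depends on assumed age effects and an assumed case mix. Secondary endpoints were not simulated, and no gain is claimed for them. This conclusion concerns the omission of age only and does not clear other features of the primary analysis.

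**What to change.** In SAP 9.2.1, add age in completed years as derived in SAP 8.7.1, as a single continuous linear term alongside the stratification factors. Keep the same covariate-adjusted risk difference, confidence interval and p-value, with no data-dependent choice of form. A further indicator for baseline Score 3 changes power by only -0.1 to +0.9 points and can be left out.

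The deadline follows from Protocol 8.10, "A Statistical Analysis Plan (SAP) will be developed and approved before the database is locked", and SAP 2.7.3, "Treatment unblinding and release of the randomization codes of the investigational product assignments for the study will occur immediately following database lock". If the interim Z has already been computed, do not rerun it; record which covariates it used. If unblinding has already occurred, keep the strata-only model as primary and report the age-adjusted model as a labelled sensitivity analysis.

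While that sentence is open, it would help to state that the as-randomised stratum is used, how ICU patients without mechanical ventilation are coded, and whether region enters.

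The cost is one more SAP version, with notification to the regulator if the primary model was agreed there. No new data are needed, and no missing values are expected because date of birth is collected at screening.

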# 9.2.2 Secondary Efficacy Endpoints

9.2.2.1 Proportion of patients achieving a category of 6 or higher at Days 14 and 28 (on a 7 point ordinal scale).

Proportion of patients achieving a category of 6 or higher at Days 14 and 28 (on a 7 point ordinal scale) will be summarized and compared using Logit model, adjusting for stratification factors.

9.2.2.2 Change in clinical status of subject at Days 14 and 28 (on a 7 point ordinal scale)

The change in clinical status of subject at Days 14 and 28 will be summarized descriptively and will be compared using rank-ANCOVA. In addition, the clinical status of subject at Days 14 and 28 will be compared using proportional odds model. .

# 9.2.2.3 All-cause mortality at Day 14

All-cause mortality at Day 14 will be summarized descriptively by treatment group. Similar analysis methods used for the primary endpoint will be applied to analyze the data from this endpoint

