## 3.2 Secondary Endpoints

The secondary efficacy endpoints for the study are:

- Proportion of patients achieving a category of 6 or higher at Days 14 and 28 (on a 7 point ordinal scale).
- All-cause mortality at Day 14
- Change in clinical status of subject at Days 14 and 28 (on a 7 point ordinal scale)
  - A 7-category ordinal scale of patient health status ranges from: 1) Death; 2) Hospitalized, on invasive mechanical ventilation or extracorporeal membrane oxygenation (ECMO); 3) Hospitalized, on non-invasive ventilation or high flow oxygen devices; 4) Hospitalized, requiring supplemental oxygen; 5) Hospitalized, not requiring supplemental oxygen; 6) Not hospitalized, limitation on activities; 7) Not hospitalized, no limitations on activities.
- Length of hospital stay (days)

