#### 8.7.4 Censoring rule for subjects with outcome of Death

For analyses of length of stay (i.e., ICU or hospitalization) or duration of mechanical ventilation all deaths within 42 days will be considered censored at Day 42. Conceptually, a death corresponds to an infinite length of stay or MV support but censoring at any time greater than or equal to Day 42 gives the same answer as censoring at Day 42; both correspond to giving deaths the worst rank.

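### SAP 9.2.2.2 analyses the ordinal secondary endpoint in two ways that rank death differently, and does not say which one carries the fixed-sequence test

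*SAP*

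**What the plan says.** SAP 3.2 lists the secondary endpoint as "Change in clinical status of subject at Days 14 and 28 (on a 7 point ordinal scale"; Protocol 8.2.2 and the synopsis use the same name. The scale is defined beneath it: "A 7-category ordinal scale of patient health status ranges from: 1) Death; 2) Hospitalized, on invasive mechanical ventilation or extracorporeal membrane oxygenation (ECMO", and further up, "4) Hospitalized, requiring supplemental oxygen".

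SAP 9.2.2.2 gives two analyses in consecutive sentences. The first works on the change score: "The change in clinical status of subject at Days 14 and 28 will be summarized descriptively and will be compared using rank-ANCOVA". The second follows directly, works on the category rather than the change, and reads: "In addition, the clinical status of subject at Days 14 and 28 will be compared using proportional odds model".

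No covariates are listed for either, although 9.2.2.1 just above adjusts for the stratification factors. SAP 8.4 protects the secondary endpoints with a fixed sequence and refers to 9.2.2 for the order. Neither section says which of the two analyses decides this step.

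SAP 8.7.4 handles deaths explicitly, reasoning that the two ways of censoring it compares "both correspond to giving deaths the worst rank". That section is limited to length of stay and duration of ventilation. No similar rule is given for the ordinal endpoint.

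**The concern.** A change score measures distance travelled, and the distance to death depends on where the patient started. A patient already ventilated at baseline can lose only one step by dying. A patient on supplemental oxygen can lose two steps and still be alive. Once these changes are ranked across all patients, some deaths rank above some survivors.

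The proportional odds model on the category does not have this property, so the two analyses can disagree. A fixed sequence needs one decision per step. If the subsection numbering in 9.2.2 is the test order, this step stands ahead of Day 14 mortality and length of stay. The choice of analysis could then decide whether those endpoints are formally tested at all. Leaving that choice open until results are seen would weaken the error control that 8.4 is meant to provide.

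**Working it through.** **The plan's own figure.** The documents give no power or sample size for this endpoint. The stated 369 completers concern Day 28 mortality and reproduce: (1.960 + 0.842)² × (0.45 × 0.55 + 0.30 × 0.70 / 2) / 0.15² = 122.97, so 123 + 246 = 369. This does not bear on the ordinal endpoint.

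**Step 1: the change scores.** Change is taken as follow-up category minus baseline category, and a patient who has died is scored 1. (The formula in SAP 8.7.3 is not legible in the text available; reversing the sign would only mirror the result.) SAP 8.5 expects baseline scores of 2, 3 and 4, for example "Baseline ordinal scale of Score 2 Critical patients" and "Baseline ordinal scale of Score 4 Severe patients".

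| Baseline | To 1 (death) | To 2 | To 3 | To 4 | To 5 | To 6 | To 7 |
|---|---|---|---|---|---|---|---|
| 2 | −1 | 0 | +1 | +2 | +3 | +4 | +5 |
| 3 | −2 | −1 | 0 | +1 | +2 | +3 | +4 |
| 4 | −3 | −2 | −1 | 0 | +1 | +2 | +3 |

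A death from 2 (−1) ranks above a survivor going 4 to 2 (−2). It ties with survivors going 3 to 2 or 4 to 3. A death from 3 (−2) ties with the 4-to-2 survivor. Reading along any row, death is the lowest value. The inversion arises only between patients with different baselines, and this step needs no assumption about rates.

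**Step 2: does a baseline covariate repair it?** This was checked in an illustrative simulation of 20,000 patients per baseline mix. All of the following are assumptions, not document figures: death risk 55%, 35% and 20% from categories 2, 3 and 4; survivors spread over categories 2 to 7 as 45/10/10/10/15/10% from category 2, 20/20/15/10/20/15% from 3, and 10/10/15/10/30/25% from 4. Entries are mid-ranks as a fraction of the sample (low is bad). Residuals are from regressing ranked change on ranked baseline.

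| Mix in 2/3/4 | Patient | Ranked change | Residual | Ranked status |
|---|---|---|---|---|
| 20/40/40% | 2 to 1, died | 0.347 | −0.146 | 0.166 |
| | 4 to 2, alive | 0.166 | −0.339 | 0.394 |
| 40/30/30% | 2 to 1, died | 0.333 | −0.168 | 0.194 |
| | 4 to 2, alive | 0.127 | −0.372 | 0.459 |
| 60/20/20% | 2 to 1, died | 0.309 | −0.188 | 0.219 |
| | 4 to 2, alive | 0.080 | −0.427 | 0.520 |

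The residual ordering stays inverted in all three mixes. The reason is that the fitted line is nearly flat. In the middle mix the fitted value is 0.333 + 0.168 = 0.501 at baseline 2 and 0.127 + 0.372 = 0.499 at baseline 4. Removing the inversion would need a difference of at least 0.333 − 0.127 = 0.206. On status, the order is correct throughout.

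**Step 3: how often pairs are affected.** In these three mixes a random death ranked above a random survivor in 1.6%, 2.3% and 2.1% of pairs, and tied in 6.1%, 6.8% and 6.1%. A separate assumed outcome table gave 2.0% inverted and 4.7% tied at Day 28, and 3.6% and 8.3% at Day 14.

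**Step 4: effect on power at Day 28.** Assumptions: 260 against 130 patients (246 against 123 in the last figure of each row), placebo mortality 45%, one third of deaths prevented, and several assumed baseline mixes and survivor tables. The comparator is a rank analysis of the category adjusted for baseline rank, used as a stand-in for the proportional odds model.

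| Where prevented deaths end up | Ranked change | Ranked status |
|---|---|---|
| Spread over survivor categories | 62%; 65–66%; 67–68% | 70%; 69–70%; 71% |
| At their baseline category | 36%; 31–33% | 46%; 38–42% |
| All alive on a ventilator | 14%; 12–19%; 11–16% | 34%; 26–32%; 26–28% |

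Other assumed mixes gave gaps as small as 1 to 2 points in the first row and 4 in the second. Adding baseline to the change analysis moved power by about one point or less. At Day 14, with placebo mortality assumed at 25%, one simulation gave 21% against 28%, 17% against 21%, and 8% against 13% for the three rows.

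**The case against.** The strongest reply is that the SAP already contains the right analysis. A reader might infer that death is not the worst outcome for this endpoint. The documents do not support that: the proportional odds model in the next sentence uses the category, where death is 1 for everyone. The statement is true of the rank-ANCOVA on change only. What remains is that the change analysis comes first and matches the endpoint's name, while nothing says which analysis decides.

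A reader might also infer that 9.2.2.2 contradicts 8.7.4. It does not, because 8.7.4 covers only length of stay and ventilation duration. It is a useful precedent for how the SAP thinks about deaths, not a conflicting rule.

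Mortality is also well covered elsewhere: Day 28 mortality is the primary endpoint, Day 14 mortality is a separate secondary endpoint, and reaching category 6 or higher is based on status. Randomization is stratified by baseline clinical status, and outright inversions are a small share of pairs. All of this stands, and it limits the point to one step of the secondary sequence. The version history records that the 9.2.2.2 method was revised to follow FDA guidance, so having two analyses looks deliberate. That still leaves open which one carries the step.

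**Conclusion.** The point holds as a gap in specification with a clear preferred answer. The two analyses in 9.2.2.2 treat death differently, the first-named one can rank a death above a survivor, a linear baseline covariate does not cure this, and the confirmatory analysis is not named. The ordering result follows from the scale alone.

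The size does not. It would be tempting to conclude that the change analysis has been shown to cost substantial power. The documents give no baseline mix, no outcome distribution and no power target for this endpoint, so the figures are only illustrative. At Day 28 the gain from analysing status is roughly 1 to 8 points if prevented deaths recover broadly, and about 4 to 10 if those patients remain at their baseline category. It reaches about 10 to 20 only if every prevented death ends on a ventilator, including patients who entered on supplemental oxygen. The primary analysis is unaffected.

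**What to change.** In SAP 9.2.2.2, make the status category the tested quantity. Suggested wording: *Clinical status at Day 14 and at Day 28 (categories 1 to 7, death = 1) will be compared with a proportional odds model adjusted for baseline category and the stratification factors. This is the confirmatory test for this step of the fixed sequence. Rank-ANCOVA on change from baseline is supportive.* State the order of the two time points in the same edit, and make the change before unblinding.

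The cost is small: the same data and a model the SAP already names. The downside is that the p-value for change, which is the protocol's name for this endpoint, is no longer the confirmatory one. The endpoint wording in Protocol 8.2.2, the protocol synopsis and SAP 3.2 should therefore be aligned with the test. If the sponsor prefers to keep change as the tested variable, ranking it within baseline category would also put death last within each baseline group. That too would have to be stated as the single confirmatory analysis.

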# 9.2.2.4 Length of hospital stay (days)

Length of hospital stays will be considered as continuous outcome and summarized descriptively.

The median length of hospital stay will be compared between the treatment groups using a non-parametric method or a rank-ANCOVA analysis i.e., an ANCOVA analysis on rank-transformed data. For this analysis, the censoring rule in Section 8.6.4 will be used.

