### 9.2.3 Exploratory Outcome Measures (Endpoints)

## 9.2.3.1 All-Cause Mortality at Day 42

All-cause mortality at Day 42 will be summarized descriptively by treatment group. Similar analysis methods used for the primary endpoint will be applied to analyze the data from this endpoint

9.2.3.2 Change in clinical status of subject at Days 3 and 7 (on a 7 point ordinal scale)

Change in clinical status of subject at Days 3 and 7 will be summarized descriptively and compared using ANCOVA adjusting for stratification factors.

If the Normality assumption is not met, a non-parametric method or a rank –ANCOVA analysis i.e., an ANCOVA analysis on rank-transformed data will be used.

9.2.3.3 Change from baseline in Sequential Organ Failure Assessment (SOFA) score at Days 3 and 7

Change from baseline in Sequential Organ Failure Assessment (SOFA) score at Days 3 and 7 will be summarized descriptively and compared using ANCOVA adjusting for stratification factors. If the Normality assumption is not met, a non-parametric method or a rank –ANCOVA analysis i.e., an ANCOVA analysis on rank-transformed data will be used.

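### SAP 9.2.2.2 and 9.2.2.4 name no stratification factors for ordinal status at Days 14 and 28 or for length of stay, so these tests may be conservative and lose power

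*SAP*

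**What the plan says.** SAP 2.5 sets the design: "Randomization will be stratified into one of the three categories based on clinical status of the patient at baseline". The categories are non-ICU, ventilated in ICU without vasopressors, and ventilated in ICU with vasopressors. Prior off-label immunomodulator use is a second factor. Protocol 8.5 adds region if sites are multinational; SAP 2.5 does not. SAP 2.4 uses blocks of 3 at 2:1.

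Two secondary endpoints have no stated covariates:

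- SAP 9.2.2.2, ordinal status at Days 14 and 28: a rank-ANCOVA on the change, followed by "In addition, the clinical status of subject at Days 14 and 28 will be compared using proportional odds model".
- SAP 9.2.2.4, length of stay: "compared between the treatment groups using a non-parametric method or a rank-ANCOVA analysis".

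SAP 9.2.1 (Day 28 mortality) and 9.2.2.1 (category 6 or above) do adjust for the stratification factors. So does the same ordinal scale at Days 3 and 7 in 9.2.3.2, which is "summarized descriptively and compared using ANCOVA adjusting for stratification factors". Length of ICU stay in 9.2.3.8 is treated likewise.

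Protocol 8.9.2 leaves the choice of covariates to the SAP. SAP 9.2 has no general adjustment sentence, and SAP 8.3 puts the stratification factor in the imputation model only. SAP 8.4 tests the secondary endpoints in a fixed sequence and points to 9.2.2 for the order.

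**The concern.** The exploratory versions of these endpoints are adjusted, while the secondary versions in the confirmatory sequence are silent. That looks unintended, and it has two consequences.

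First, several different p-values would satisfy the text. A rank-ANCOVA needs a covariate and none is named. An unadjusted rank test for length of stay would also comply.

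Second, stratified blocks balance the arms on severity. An analysis that ignores severity still counts the between-stratum spread as noise, so its nominal 5% test rejects less than 5% of the time under the null and loses power. In a proportional odds model, omitting prognostic strata also pulls the estimated odds ratio towards 1.

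If the order of 9.2.2 is the test order, ordinal status is second. A missed test there would block Day 14 mortality and length of stay.

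**Working it through.** **1. The plan's own figure.** The only stated power is for the primary endpoint: "This sample size is based on using a 2-sided Z-test with 80% power and an overall significance level of 0.05", with "15% which is 45% Day 28 mortality rate for the placebo group versus 30% Day 28 mortality rate in the leronlimab group". The unpooled two-proportion formula at 2:1 gives

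placebo n = (1.960 + 0.842)² × [0.45×0.55 + (0.30×0.70)/2] / 0.15² = 7.85 × 0.3525 / 0.0225 ≈ 123.

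This matches "369 subjects (246 subjects in the leronlimab and 123 in the placebo group) complete the study". Then 123/0.95 rounds up to 130, and 130 × 3 = 390 randomised. The sample size is sound. No power is stated for the two secondary endpoints.

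**2. Mechanism.** Let R² be the share of rank variance lying between strata. With strata balanced by design, the true variance of the treatment contrast is about (1 − R²) times what an unadjusted test assumes. SAP 9.2 says "All statistical tests for efficacy will be two-sided tests" at 0.05, so true size ≈ 2Φ(−1.96/√(1 − R²)). For illustration:

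- R² = 0.15: 2Φ(−2.13) ≈ 3.3%.
- R² = 0.30: 2Φ(−2.34) ≈ 1.9%.

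**3. Simulation, proportional odds.** From the documents: 369 completers, 2:1, blocks of 3, and six strata (three clinical × two immunomodulator). Assumed:

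- clinical strata 60/25/15%, and 30% prior immunomodulator use;
- treatment odds ratio 1.8;
- a seven-category outcome with about 25% in the worst category at average risk;
- a prognostic log-odds shift for ventilated versus non-ICU as tabulated, half as much again with vasopressors, and 0.2 for prior immunomodulator use.

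There were 2,500 trials per cell. The Monte Carlo standard error is about 0.4 points on size and 0.8 on power.

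| Strata (log-OR) | Size, unadjusted | Size, adjusted | Power, unadjusted | Power, adjusted | Gain (points) |
|---|---|---|---|---|---|
| None (0) | 5.2% | 5.3% | 83.2% | 83.0% | about 0 |
| Weak (0.5) | 5.5% | 6.0% | 82.8% | 83.7% | about 1 |
| Moderate (1.2) | 3.3% | 4.8% | 74.8% | 81.0% | about 6 |
| Strong (2.0) | 2.0% | 5.8% | 58.2% | 75.6% | about 17 |
| Strong, shares 85/10/5% | 3.2% | 4.6% | 72.9% | 79.9% | about 7 |

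The mean log odds ratio is 0.59 adjusted. Unadjusted it falls to 0.53 (moderate), 0.51 (strong, 85% non-ICU) and 0.44 (strong). In the strong case that is exp(0.59) = 1.80 against exp(0.44) = 1.55. The 6.0% adjusted size with weak strata is a little over two standard errors high. The unadjusted test in the same trials is also high, at 5.5%.

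**4. Simulation, rank test on final status (power, with size in brackets).**

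| Strata | No covariate | Baseline score | Stratification factors |
|---|---|---|---|
| Moderate | 74.8% (3.3%) | 78.0% (4.4%) | 79.7% (4.7%) |
| Strong | 58.6% (2.0%) | 70.0% (5.4%) | 73.6% (5.9%) |
| Strong, 85% non-ICU | 73.2% (3.2%) | 75.2% (4.1%) | 78.8% (4.6%) |

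Baseline score alone recovers 3.2 of 4.9 points, 11.4 of 15.0, and 2.0 of 5.6.

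**5. A second set of assumptions.** This used 390 subjects, three clinical strata at 65/25/10%, common odds ratio 1.82, a rank test and 6,000 runs.

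| Placebo mortality by stratum | Power, unadjusted | Power, adjusted | Size, unadjusted |
|---|---|---|---|
| 39/53/60% | 85.2% | 86.0% | 4.4% |
| 35/62/75% | 80.4% | 83.3% | 4.4% |
| 30/72/85% | 71.0% | 79.6% | 2.6% |

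The direction agrees, and the loss grows with the prognostic strength of the strata.

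Length of stay was not simulated. The rank-test result is carried over because SAP 8.7.4 gives deaths the worst rank. The rank-ANCOVA on change was not simulated either; step 4 ranks final status.

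**The case against.** Silence is not a decision to leave the strata out. Rank-ANCOVA implies at least one covariate, most naturally baseline score, which overlaps the severity strata; step 4 shows this reduces the loss. The length-of-stay wording follows Protocol 8.10.4. The size of the effect rests on inputs the documents do not give. Eligibility may also narrow the prognostic range: intubated subjects must meet PEEP and PaO2/FiO2 limits, and prolonged vasopressor use above the dose that defines the third stratum is excluded. The proportional odds comparison is introduced as an addition, so it may not be the gatekeeping test. The error is conservative.

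All of this limits the size of the point. None of it supplies the missing covariates, and baseline score in the rank-ANCOVA would not help the proportional odds model or an unadjusted length-of-stay test.

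Three stronger readings are tempting, and the documents do not support them:

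- A reader might infer that these are the only efficacy analyses without stated adjustment. Day 14 and Day 42 mortality are adjusted only by reference to the primary method. The rank fallbacks in 9.2.3 do not restate adjustment. The pooled open-label efficacy analysis in 9.4 names no model.
- A reader might infer that a substantial power loss is established. With weak strata it is about one point or less.
- A reader might infer that a failure on either endpoint ends later claims. Length of stay is last in 9.2.2, so its failure blocks nothing.

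**Conclusion.** The point holds as a gap in specification with a possible cost in power. Neither section names the stratification factors, and no other text supplies them. Run as written, the proportional odds model and an unadjusted rank test for length of stay would be conservative wherever severity predicts outcome.

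Under the assumptions shown, the proportional odds loss runs from about 1 point (weak strata) to about 6 to 17 points (moderate to strong). True size is about 2 to 3% in the latter settings. The rank-ANCOVA loses less if it carries baseline score, which the SAP does not state. The size for length of stay is inferred, not computed.

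Type I error is not inflated and the primary analysis is unaffected. The fixed-sequence consequence applies to ordinal status only. This is a free improvement, not a threat to validity.

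**What to change.** - **SAP 9.2.2.2:** state that both the rank-ANCOVA and the proportional odds model adjust for the stratification factors, and that the rank-ANCOVA also carries baseline ordinal score. Say which of the two is the confirmatory test in the fixed sequence.
- **SAP 9.2.2.4:** specify rank-ANCOVA adjusting for the stratification factors, and delete the alternative of an unspecified non-parametric method. This stays within the options in Protocol 8.10.4.
- **SAP 2.5:** reconcile with Protocol 8.5 on region, so that the models use the factors actually used to randomise.
- **Reporting:** note that the adjusted proportional odds model estimates a conditional odds ratio, not a marginal one.

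The cost is a few sentences, made before the treatment codes are released. It needs no new data or extra subjects, and the SAP already uses this adjustment elsewhere.
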